12.2.1 Sensitivity Analyses

Any planned sensitivity analyses will be documented in the SAP prior to database lock.

12.2.2 Imputation of Missing Data

All data will be used according to availability, with no imputation for missing data.

12.3 DEFINITION OF POPULATIONS

12.3.1 Randomized Population

All subjects who are randomized.

12.3.2 Safety Population

All subjects who have had at least one dose of study drug and one subsequent contact with the Investigator will be analyzed for safety.

12.3.3 Full Analysis Set

All subjects who have had at least one dose of study drug and who have at least one evaluable post-dose PK sample will be included in the FAS population. This population will be utilized for the PK Analysis.

13 ETHICAL CONSIDERATIONS

The Sponsor and Investigator must comply with this protocol, all applicable national and local regulations including International Conference on Harmonization (ICH) and Good Clinical Practice (GCP).

13.1 DECLARATION OF HELSINKI

The Sponsor and the Investigator must comply with the principles set forth by the Declaration of Helsinki dated October 2008.

13.2 INSTITUTIONAL REVIEW BOARD / INDEPENDENT ETHICS COMMITTEE

The Investigator must ensure that the IRB/IEC has approved the protocol, the Information Sheet and Consent Form and any other required study documents prior to starting the study. The Sponsor must approve any changes to the Information Sheet and Consent Form before submission to the IRB/IEC.

Prior to activation of a site and provision of IMP, the Sponsor must receive documentation to demonstrate IRB/IEC approval of the required study documents and must have completed a comprehensive site initiation training with the Investigator and site staff.

A progress report must be submitted to the IRB/IEC at least annually and more frequently if required by the IRB/IEC.

On completion or termination of the study the Investigator or Sponsor must submit a closeout letter to the IRB/IEC (as required). A copy of the CSR synopsis will also be sent in accordance with local laws.

13.3 SUBJECT INFORMATION AND INFORMED CONSENT

IRB/IEC approval of the written information sheet and consent form must be obtained prior to use. The Information Sheet will provide the subject with a complete and comprehensive explanation of the study including the study rationale, the procedures, the benefits and risks, that participation is voluntary and that the subject may withdraw from the study at any time without any negative consequences. In addition, a physician will discuss this information with the subject who will be given sufficient time and opportunity to have any questions answered and to make a decision of whether to participate in the study.

Written informed consent must be obtained from the subject in accordance with local practice and regulations prior to any study assessment or test being conducted. Written consent will be obtained by signing and dating the IRB/EC approved consent forms.

Each consent form must also contain an authorization for the Sponsor and Investigators to use and disclose Protected Health Information (PHI) in compliance with local law.

No study assessments or procedures should be conducted until written informed consent has been provided.

A copy of the information sheet and consent form signed and dated by the subject must be given to the subject. The signed consent form(s) will be retained with the study records at site. A description of the consent process must be documented in the subject's medical record.

13.4 SUBJECT DATA PROTECTION

Prior to any study test being conducted, including Screening tests, the subject must provide authorization as required by local law, eg. PHI. Subjects will not be identified by name (or initials) in the eCRF or any study reports. Data will be used for research purposes only. Every effort will be made to keep the subject's personal medical data confidential. All data will be used for research purposes only.

13.5 SUBJECT INSURANCE

The Sponsor maintains appropriate insurance coverage for clinical trials and will follow applicable local compensation laws.

13.6 CONFLICT OF INTEREST

Investigators should address any potential conflicts of interest (e.g. financial interest in the Sponsor) with the subject before the subject makes a decision to participate in the study.

13.7 REGISTRATION OF STUDY AND DISCLOSURE OF RESULTS

The Sponsor will register the study on all required registries (e.g. clinicaltrials.gov) and will post study results regardless of outcome on publicly accessible websites in accordance with the applicable laws and regulations.

14 STUDY MANAGEMENT

14.1 SOURCE DATA

The Investigator must ensure that all source documents (i.e., medical records) and eCRF pages are completed and maintained according to the study protocol and are available at the site.

The Investigator should ensure clear records are maintained that demonstrate the integrity of the data reported to the Sponsor via the eCRF. This includes all original records, certified copies of clinical findings, observations or other activities necessary for reconstruction and evaluation of the study. This includes, but is not limited to, Investigator signed/dated laboratory reports and medical notes. Source data must not be changed without clear and documented rationale. Any changes should be confirmed with the originator. A full audit trail should always be available to identify the person making the entry and/or amendments, the original entry/result, the amendment and rationale. The Investigator must ensure that source data is always attributable, legible, contemporaneous, original and accurate.

For this study, key data reported on eCRFs will be verified against source documents. The eCRF will not act as source except in the instance of laboratory data which will be transferred directly to the Sponsor/designee responsible to Data Management.

14.2 QUALITY ASSURANCE

During and/or after study completion, Sponsor quality assurance officers, IRB/IEC or regulatory authorities may perform on-site audits. The Investigator will be expected to cooperate with any audit by providing assistance and access to all requested study-related records.

14.3 MONITORING

The Investigator must permit study-related monitoring by providing direct access to source data and to the subjects' medical records. The Monitor(s) will visit the Investigator at regular intervals during the course of the study and after completion of the study if needed.

During the monitoring visits, eCRFs, source records and other documentation relating to the study will be made available for review. The Investigator will ensure any discrepancies or omissions are resolved.

Monitoring visits must be conducted according to the applicable ICH and GCP guidelines to ensure protocol adherence, data quality, IMP accountability, compliance with IRB/IEC/regulatory requirements and continued adequacy of the investigational site, resources and its facilities to conduct the study.

Frequency and scope of the monitoring visits will be defined in the Clinical Monitoring Plan which will also define the extent of source data verification to be conducted.

14.4 STUDY FUNDING

Shield TX (UK) Limited is the Sponsor and provides funding for the conduct of this study. All financial details are provided in clinical trial agreements between the institution, Investigator and Sponsor.

14.5 CONTRACT RESEARCH ORGANIZATION (CRO)

A CRO (Medpace Inc.) will be contracted to be responsible for administrative aspects of the study including, but not limited to, site selection and qualification, study set-up, site initiation, monitoring, data management including clinical database and electronic CRF provisioning, statistics and programming and study reporting. Vendors will also be contracted to cover supportive services such as a central laboratory, bioanalysis of PK samples and IMP production/labelling.

14.6 AMENDMENTS TO THE STUDY PROTOCOL

The study will be conducted in compliance with this Protocol, as approved by all relevant parties. Should any amendments to the protocol be deemed necessary, this will be resolved by mutual written agreement between the Principal Investigator and the Sponsor.

Any significant changes to the protocol shall be submitted to the IRB/IEC and Regulatory Authorities and must be approved prior to implementation as required by local law.

However, the Sponsor may, at any time, amend this protocol to eliminate an apparent immediate hazard to a subject. In this case, appropriate communications and notifications to the IRB/IEC and Regulatory Authorities will occur as required by local law.

Amendments to the Information Sheet and Consent Form will be made if impacted by an amendment to the study protocol which will also be submitted and approved to the IRB/IEC as required by local law.

14.7 STUDY STOPPING RULES

The Sponsor may terminate this study at any time. In consultation with the Investigator it is normal procedure to review the emerging clinical and safety data (section 7.6). As a result of this review it may be necessary to stop the study before all subjects have completed the study. In this case, all subjects will be followed-up for safety assessments.

The Sponsor will notify the IRB/IEC of discontinuation of the study and the reason for doing so.

14.8 END OF STUDY

The end of study is the date of the last subject, last visit for final collection of data.

14.9 RETENTION OF RECORDS

The Investigator must retain the informed consent documentation, disposition of the IMP, hard-copy eCRFs, medical records and other source data for at least 25 years after completion or discontinuation of the trial or for at least 2 years after the granting of the last marketing authorization in the EC (when there are no pending or contemplated marketing applications in the EC) or for at least 2 years after formal discontinuation of clinical development of the investigational product. Prior to proceeding with destruction of records, the Investigator must notify the Sponsor in writing and receive written authorization from the Sponsor to destroy study records.

The Investigator must also notify the Sponsor of any changes in the archival arrangements including, but not limited to, archival at an off-site facility or transfer of ownership if the Investigator leaves the site.

In addition, the Sponsor will retain copies / originals (as appropriate) of any study-related documents in the Trial Master File until at least 2 years after the last approval of a marketing application in an ICH region, until there are no pending or contemplated marketing applications in an ICH region or at least 2 years have elapsed since the formal discontinuation of clinical development of the investigational product.

14.10 SECURITY AND PUBLICATIONS

This study protocol remains the Sponsor property until the final fulfilment of the contract and may only be passed on to registration authorities and license partners with the Sponsor / Applicant's approval. The study site will treat all knowledge about the study product and/or its manufacturer with strictest confidentiality.

The Sponsor ensures that substances used in the manufacture of the IMP are generally known in pharmaceutical science and have been released by the appropriate national authorities for use in medications, cosmetics or food.

Publication rights will be described in the Investigator contract. The study site's agreement is not required for using the study results for discussions with regulatory/governmental authorities or for other purposes such as presentation at conferences, discussion with potential licensing partners or specialist groups.

ECG	Electrocardiogram
eGFR	Estimated Glomerular Filtration Rate
FDA	Food and Drug Administration
GCP	Good Clinical Practice
GGT	Gamma-Glutamyl Transpeptidase
GI	Gastrointestinal
hr	Hour
Hb	Hemoglobin
HIV	Human Immunodeficiency Virus
IBD	Inflammatory Bowel Disease
ICH	International Conference on Harmonization
ID	Iron Deficiency
IDA	Iron Deficiency Anemia
IEC	Independent Ethics Committee
IMP	Investigational Medical Product
IRB	Institutional Review Board
IRT	Interactive Response Technology
IUD	Intrauterine Contraceptive Devices
IV	Intravenous
MAA	Marketing Authorization Application

Abbreviation	Definition
NCS	Non-Clinically Significant
NTBI	Non-Transferrin Bound Iron
OFP	Oral Ferrous Product
PHI	Protected Health Information
PIP	Pediatric Investigational Plan
PK	Pharmacokinetics
PSP	Pediatric Study Plan
SAE	Serious Adverse Event
SAP	Statistical Analysis Plan
SARS-CoV-2-RT-PCR	Severe Acute Respiratory Syndrome-associated Coronavirus RealTime Reverse Transcriptase-Polymerase Chain Reaction
SD	Standard Deviation
TEAE	Treatment-emergent Adverse event
TESAE	Treatment-emergent Serious Adverse event
TIBC	Total Iron Binding Capacity
TLAG	The delay between the time of dosing and time of appearance of concentration in the sampling compartment
T_{max}	Time to Maximum Plasma Concentration
TNF-a	Tumor Necrosis Factor alpha
TSAT	Transferrin Saturation
$T_{1/2}$	Apparent terminal elimination half-life
UC	Ulcerative Colitis
UIBC	Unsaturated Iron Binding Capacity
WHO	World Health Organization
yrs	Years
λ_z	Apparent terminal elimination rate constant, determined by linear regression of the terminal points of the ln-linear plasma concentration-time curve

1 INTRODUCTION

This statistical analysis plan (SAP) provides a detailed, technical elaboration of the statistical analyses of pharmacokinetic (PK) and safety data as described in the study protocol 2.0 dated 15 July 2020. Specifications for tables, listings, and figures are contained in a separate document. Any deviation from this analysis plan will be substantiated by sound statistical/PK/PD rationale and will be documented in the final clinical study report.

2 STUDY OVERVIEW

2.1 Study Objectives

2.1.1 *Primary Objective*

The primary objective is to evaluate the pharmacokinetics (PK) of iron absorption after a single 30 mg dose of ferric maltol administered as capsule or oral suspension in fasted and fed conditions, via primary parameters C_{max} and AUC_{last} .

2.1.2 *Secondary Objectives*

The secondary objectives are:

To evaluate the pharmacokinetics (PK) after a single 30 mg dose of ferric maltol administered as a capsule or oral suspension (fasted and fed conditions); through measurements of transferrin saturation (TSAT), baseline corrected serum iron, transferrin, total and unsaturated iron binding capacity (TIBC and UIBC), and plasma of maltol and maltol glucuronide.

To assess the safety and tolerability of ferric maltol after a single dose of 30 mg administered as a capsule or oral suspension (fasted and fed conditions); based on vital signs, adverse events, concomitant medications and routine clinical laboratory safety blood tests.

2.2 Study Design

2.2.1 *Study Overview*

This is a Phase I, randomized, open-label, single dose, four-way crossover study, to compare the pharmacokinetics of iron and maltol absorption from ferric maltol capsules and oral suspension formulations under fasted and fed conditions in adult healthy volunteers.

A total of 32 eligible subjects will be randomized at a ratio of 1:1:1:1 to receive one of the following treatment sequences comprised of four treatment periods. Treatment periods will last 4 days with at least 48 hours washout period between each dose administration. Eight subjects will be randomized to each treatment sequence:

Sequence A:

- Period 1; single dose of 30 mg ferric maltol capsule in a fed condition
- Period 2; single dose of 30 mg (5 ml) ferric maltol suspension in a fed condition
- Period 3; single dose of 30 mg ferric maltol capsule in a fasted condition
- Period 4; single dose of 30 mg (5 ml) ferric maltol suspension in a fasted condition

Sequence B:

- Period 1; single dose of 30 mg (5 ml) ferric maltol suspension in a fasted condition
- Period 2; single dose of 30 mg ferric maltol capsule in a fed condition
- Period 3; single dose of 30 mg (5 ml) ferric maltol suspension in a fed condition
- Period 4; single dose of 30 mg ferric maltol capsule in a fasted condition

Sequence C:

- Period 1; single dose of 30 mg ferric maltol capsule in a fasted condition
- Period 2; single dose of 30 mg (5 ml) ferric maltol suspension in a fasted condition
- Period 3; single dose of 30 mg ferric maltol capsule in a fed condition
- Period 4; single dose of 30 mg (5 ml) ferric maltol suspension in a fed condition

Sequence D:

- Period 1; single dose of 30 mg (5 ml) ferric maltol suspension in a fed condition
- Period 2; single dose of 30 mg ferric maltol capsule in a fasted condition
- Period 3; single dose of 30 mg (5 ml) ferric maltol suspension in a fasted condition
- Period 4; single dose of 30 mg ferric maltol capsule in a fed condition

The planned study consists of three study phases:

1. Screening Phase;
2. Treatment Phase;
3. Follow-Up Phase.

Table 1 contains details of the study periods, study visits and timing of the visits.

Table 1 Study Visits

Phase	Period	Study Visit	Study Day
Screening	Screening	1	-14 to -1
Treatment	Treatment Period 1	2	1
	Treatment Period 2	3	3
	Treatment Period 3	4	5
	Treatment Period 4	5	7
Follow-Up	Follow-Up	6	10-14

The Screening Phase will consist of one visit: Study Visit 1 (Screening) scheduled to take place within 14 days prior to the planned Treatment Phase for each subject. The purpose of this visit is to determine subject eligibility for the study.

Prior to the first treatment period, subjects will arrive at the Clinical Unit on Day -1 at least 13 hours before dosing. After at least 10 hours overnight fasting at the Clinical Unit subjects will be randomized to one of the 4 treatment sequences. PK samples will be collected pre-dose and up to 24 hours post-dose during each period (12 times including pre-dose) for the measurements of serum iron, TSAT, TIBC, UIBC, transferrin, plasma maltol and maltol glucuronide.

There will be at least 48 hours washout period between dose administrations. Subjects will fast at least 10 hours prior to each treatment period dosing.

Subjects will stay at the Clinical Unit during the 4 treatment and 3 washout periods and will be discharged on Day 8 following the last PK sampling timepoint.

Post study telephone follow-up will be conducted 3-7 days following Treatment Period 4. During early discontinuation a safety follow up at the Clinical Unit will be performed 3-7 days after the last study medication.

The schedule of procedures can be found in Table 10.2 from Protocol.

2.2.2 *Treatment Assignment and Blinding*

This is an open label study and treatment assignment is not blinded.

The randomization procedure (created using a computer-generated random permutation procedure) will randomize the subject to one of the 4 treatment sequences to either Sequence A Sequence B, Sequence C or Sequence D. The site will dispense the appropriate formulation of open-label ferric maltol bottles at each scheduled PK day according to the schedule of assessments. The randomization scheme will be programmed by Medpace independent statistician using SAS®. Detailed randomization methods and procedures are described in a stand-alone document.

2.2.3 *Study Drug*

Investigational Medicinal Product

Ferric maltol oral suspension: oral suspension containing 30 mg elemental iron, in the form of 231.5 mg ferric maltol, in 5 ml suspension.

Comparator

Ferric maltol capsules: gelatin capsules with 30 mg elemental iron, in the form of 231.5 mg ferric maltol.

2.2.4 *Sample Size Determination*

The sample size is based on the comparisons of each of the primary PK parameters C_{max} and AUC_{last} for total serum iron between the formulations for each of the two conditions: fed and fasted. Each comparison will be made via the ratio of the two values of the parameter between the formulations. The 90% confidence interval (CI) for this ratio will be reported.

Thus, there are 4 primary endpoints:

In fed condition

C_{max} (suspension) / C_{max} (capsule)

AUC_{last} (suspension) / AUC_{last} (capsule)

In fasted condition

C_{max} (suspension) / C_{max} (capsule)

AUC_{last} (suspension) / AUC_{last} (capsule)

Data from a previous study (ST10-01-101) were used to provide estimates of the standard deviations (SDs) of the logs of the within-subject ratios of the parameters C_{max} and AUC_{last} (between formulations). Assuming the SD is no greater than 0.38, and that the true ratio is 1, 20 subjects would provide a probability of at least 80% of each individual confidence interval lying

within (80%, 125%). Further if all the 4 ratios to be reported are independent, 31 subjects would provide probability of at least 80% of all 4 confidence intervals lying within (80%, 125%). As the SD is uncertain, 32 subjects will be recruited in the study.

The target recruitment number is 32 and up to an additional 4 may be recruited to replace early withdrawing subjects.

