Thus, there are 4 primary endpoints:

In fed condition

$$C_{max}(\text{suspension}) / C_{max}(\text{capsule})$$

$$AUC_{last}(\text{suspension}) / AUC_{last}(\text{capsule})$$

In fasted condition

$$C_{max}(\text{suspension}) / C_{max}(\text{capsule})$$

$$AUC_{last}(\text{suspension}) / AUC_{last}(\text{capsule})$$

Data from a previous study (ST10-01-101) were used to provide estimates of the standard deviations (SDs) of the logs of the within-subject ratios of the parameters C_{max} and AUC_{last} (between formulations). Assuming the SD is no greater than 0.38, and that the true ratio is 1, 20 subjects would provide a probability of at least 80% of each individual confidence interval lying within (80%, 125%). Further assuming that all the 4 ratios to be reported are

independent, 31 subjects would provide probability of at least 80% of all 4 confidence intervals lying within (80%, 125%). As the SD is uncertain, 32 subjects will be recruited in the study.

Statistical Methods

For each of total serum iron, baseline corrected serum iron, maltol, maltol glucuronide, TSAT, TIBC, UIBC and transferrin, concentration data will be listed for each individual subject, by formulation and condition (fed / fasted). The data will be summarized, for each of the four formulations/conditions, at each time point by using the following descriptive statistics: n (the number of subjects), arithmetic mean, standard deviation (SD), geometric mean, coefficient of variation (CV), median, minimum and maximum, and a 90% confidence interval (CI) for the mean.

Concentration-time courses of each analyte will be graphically displayed per subject. For each feeding condition, plots of the geometric mean concentration and its 90% CI, versus time, by formulation, will be provided, overlaid.

For serum iron, baseline corrected serum iron, maltol, maltol glucuronide, TSAT, TIBC, UIBC and transferrin, the PK parameters (C_{max} , T_{max} , AUC_{last} , AUC_{inf} , λ_z , $t_{1/2}$) will be listed and summarized, for each of the four formulations/conditions, using the following descriptive statistics: n, arithmetic mean, SD, geometric mean, CV, median, minimum and maximum.

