12 STATISTICAL CONSIDERATIONS

12.1 SAMPLE SIZE AND POWER CALCULATIONS

The sample size is based on the comparisons of each of the primary PK parameters C_{max} and AUC_{last} for total serum iron between the formulations, within each of the two conditions: fed and fasted. Each comparison will be made via the ratio of the two values of the parameter between the formulations. The 90% confidence interval (CI) for this ratio will be reported.

For each of the two comparisons (suspension vs capsule (fed condition); suspension vs capsule (fasted condition)) the CIs for two parameter ratios (C_{max} and AUC_{last}) for serum iron will be calculated, making a total of 4 CIs. If these ratios were all independent, and the probability of being within (80%, 125%) was 80% for each, then the probability that all 4 would fall within the required limits would be $(80\%)^4 = 41\%$. With individual probabilities of 90%, the combined probability would be 66%. However, if the ratios were positively correlated, the combined probabilities would be higher.

Data from a previous study (ST10-01-101) were used to provide estimates of the standard deviations (SDs) of the logs of the within-subject ratios of the parameters C_{max} and AUC_{last} , for both total serum iron and TSAT. Assuming the SD is no greater than 0.38, if the true ratio is 1, 31 subjects would provide a probability of at least 80% of all 4 CIs lying within (80%, 125%).

The aim of the study is to demonstrate that the 4 CIs for serum iron are all within (80%, 125%). As the SD, and the degree of correlation, are uncertain, 32 subjects will be recruited to the study.

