3.5.5 PK analysis

To compare the pharmacokinetics of ferric maltol capsules and oral suspension under fasted and fed conditions, a subject must have a calculable PK parameter for both formulations under fasted or fed condition.

An ANOVA model will be performed on the ln-transformed PK parameters (C_{\max} , AUC_{last} and AUC_{inf}) of the two formulations including terms for sequence (treatment sequence), treatment (formulation/condition), and period as fixed effects, and subjects nested within a sequence as a

random effect. The estimates will be back-transformed into original scale. The point estimates for ratios and the corresponding 90% CIs will be provided.

The PK parameters analyses will be based on the FAS Population.

The sample SAS code for this analysis is included here for $\alpha = 0.10$:

```
proc mixed;
  class subject treatment sequence period;
  model logPKvar = treatment sequence period /ddfm=Satterthwaite; random
  subject(sequence);
  lsmeans treatment/pdiff cl alpha=0.1;
  run;
```

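### The stated power does not follow from a 90% CI: at SD 0.38 and true ratio 1, 20 subjects give 62–66% for one CI and 31 give 60–63% for all four if independent, not at least 80%

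*SAP*

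**What the plan says.** SAP 2.2.4 and the sample size part of the Protocol Synopsis set out the same calculation. There are four primary comparisons: Cmax and AUClast of total serum iron, suspension over capsule, each under fed and fasted conditions. The interval is fixed: "The 90% confidence interval (CI) for this ratio will be reported". The SD is that of the log within-subject ratio ("standard deviations (SDs) of the logs of the within-subject ratios of the parameters"), and the planning values are "Assuming the SD is no greater than 0.38, and that the true ratio is 1".

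Two claims follow:

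- **One interval:** "20 subjects would provide a probability of at least 80% of each individual confidence interval lying within (80%, 125" per cent limits (Synopsis; the SAP has the same sentence).
- **All four, assuming independence:** "31 subjects would provide probability of at least 80% of all 4 confidence intervals lying within (80%, 125" per cent limits (SAP; the Synopsis says the same).

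Protocol 12.1 repeats the second claim as "31 subjects would provide a probability of at least 80% of all 4 CIs lying within (80%, 125" per cent limits, without tying that sentence to independence. It also makes all four intervals within the limits the aim of the study, and it notes that positive correlation would raise the joint probability. The planned number is 32, with up to 4 replacements. The SAP 3.5.5 code uses the same interval level: "lsmeans treatment/pdiff cl alpha=0.1".

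**The concern.** Every input needed to check the two claims is in the documents, and the results fall well short of 80%.

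Protocol 12.1 itself gives a quick warning. It correctly says that 90% per interval gives 66% for four independent intervals. To reach 80% for all four, each interval needs 0.80^(1/4) = 94.6%, and 31 subjects do not deliver that at SD 0.38.

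The joint probability is the operating characteristic that matters, because all four intervals are the study aim and the results are meant to support interchangeability of capsule and suspension. A reader is told that, with identical products and the SD at its planning bound, the aim is missed at most one time in five. If the real figure is nearer one in three, a failed interval means something different.

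**Working it through.** **Inputs**

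- 90% CI, so 5% per side (SAP 2.2.4; SAP 3.5.5 code).
- Limits 80–125%, or ±ln(1.25) = ±0.2231 on the log scale.
- SD of the log within-subject ratio 0.38, so SE = 0.38/√n.
- True ratio 1.
- For four intervals, independence (Synopsis; SAP 2.2.4).

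**Formula.** With true log-ratio 0 and estimated standard error *s*, the interval is mean ± t(0.95, df)·*s*. The probability that it lies within ±0.2231 is 2Φ[(0.2231 − t·s)/SE] − 1 (zero if negative), averaged over the chi-square distribution of *s*. I use df = n − 1 for the paired analysis. For the SAP mixed model I use df = 3n − 6, assuming a common residual variance; the SE is the same. Four independent intervals have probability p⁴.

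**Hand check, normal approximation**

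- n = 20: SE = 0.38/√20 = 0.0850; 0.2231/0.0850 = 2.626; 2.626 − 1.645 = 0.981; 2Φ(0.981) − 1 = 67%.
- n = 31: SE = 0.0682; 0.2231/0.0682 = 3.27; less 1.645 = 1.625; 2Φ(1.625) − 1 = 89.6%; 0.896⁴ = 64%.

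Even this approximation, the most favourable of the two-limit methods tried, does not reach 80%.

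**Exact results**

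| n | Quantity | Stated | Paired | Mixed model |
|---|---|---|---|---|
| 20 | one CI | ≥80% | 62.4% | 65.7% |
| 31 | one CI | – | 87.9% | 89.0% |
| 31 | all four, independent | ≥80% | 59.6% | 62.8% |
| 32 | one CI | – | 89.1% | 90.1% |
| 32 | all four, independent | – | 63.0% | 66.0% |

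The mixed-model joint figures are approximate, because fed and fasted intervals for one parameter share a residual variance; the effect is about 0.1 point. A simulation of 400,000 paired trials gave 62.5% (n = 20, one CI) and 59.9% (n = 31, four CIs).

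**What would make the claims true**

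- *Larger n at SD 0.38:* 27 subjects for one CI (26 mixed) and 39 for four independent CIs (38 mixed).
- *Smaller SD (paired):* at most 0.329 for one CI at n = 20; at most 0.340 for four at n = 31. At n = 32 the limit for four is 0.345 (0.35 mixed).

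**Correlation.** Suppose Cmax and AUClast are perfectly correlated within a condition and the two conditions are independent. The joint probability is then p²: 77.2% (79.2% mixed) at n = 31 and 79.4% (81.3%) at n = 32. With a within-condition correlation of 0.5, 0.8 or 0.9, simulation of the paired analysis gives about 62%, 67% and 70% at n = 31, and 66%, 70% and 72% at n = 32. If all four were perfectly correlated, the ceiling is the single-CI figure, 89–90% at n = 32.

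**Reproducing 20 and 31.** At 10% per side (an 80% CI), the exact paired calculation gives 77.7% at n = 19 and 80.2% at n = 20 for one CI. For four independent CIs it gives 78.4% at n = 30 and 80.7% at n = 31. So 20 and 31 are exactly the smallest sizes for an 80% CI. The documents name no formula or software, so this explanation is an inference.

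**The case against.** Four points can be made for the plan.

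1. **0.38 is an upper bound.** True, and power rises quickly below it: at n = 32 the paired four-interval figure under independence is 82% at SD 0.34 and 86% at 0.33. But a promise of at least 80% for any SD up to 0.38 has to hold at 0.38, and it does not.
2. **Independence is pessimistic.** Cmax and AUClast come from the same profile, and Protocol 12.1 does not tie its 31-subject sentence to independence. That sentence is therefore less directly contradicted, but it still needs strong correlation between fed and fasted ratios as well. The Synopsis and SAP 2.2.4 state independence as the premise, and correlation has no bearing on the 20-subject claim.
3. **32 subjects are planned, not 31.** This adds about 3 points under independence. The 4 extra subjects only replace early withdrawals.
4. **Nothing in the analysis changes.** Correct: estimates, intervals and populations are unaffected, and each interval alone still has 89–90% power at n = 32. This limits the consequence but does not make the stated figures right.

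**Conclusion.** The concern holds. At the plan's own inputs (90% CI, both limits, SD 0.38, true ratio 1), the single-interval claim is short by about 14–18 points and the four-interval claim by about 17–20 points under independence. The ranges span the paired analysis and the SAP mixed model.

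At the planned 32 subjects the chance of missing the study aim with identical products is:

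- about 34–37% if the four ratios are independent;
- about 19–21% if Cmax and AUClast are perfectly correlated within condition and the conditions are independent;
- about 10–11% if all four are perfectly correlated.

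These figures assume 32 subjects evaluable for every comparison. A true ratio other than 1 lowers all of the power figures. What fails is the worst-case assurance, not the validity of the analysis.

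**What to change.** In the Protocol Synopsis, Protocol 12.1 and SAP 2.2.4, delete the 20- and 31-subject claims where they appear and put in their place, in substance:

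> At SD 0.38 and true ratio 1, 32 subjects give about 89–90% probability that each 90% CI lies within (80%, 125%). For all four the probability is about 63–66% if independent, rising to about 79–81% if Cmax and AUClast are perfectly correlated within condition. Reaching 80% for all four under independence requires an SD of no more than about 0.345–0.35.

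The Protocol 12.1 sentence that 90% per interval gives 66% jointly is correct and can stay.

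The cost is wording in three places and a less favourable power statement; enrolment and analysis stay as they are. If the sponsor wants 80% for all four at SD 0.38 under independence, that takes 38–39 subjects. Otherwise the text should say why a smaller SD, a stated correlation or a lower joint probability is acceptable.
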